2.3.4. Management of Study Quality

The Sponsor will implement a system to manage the quality of the study, focusing on processes and data that are essential to ensuring participant safety and data integrity. Prior to study initiation, the Sponsor will identify potential risks associated with critical trial processes and data and will implement plans for evaluating and controlling these risks. Risk evaluation and control will include the selection of risk-based parameters (e.g., adverse event rate, protocol deviation rate) and the establishment of quality tolerance limits for these parameters prior to study initiation. Detection of deviations from quality tolerance limits will trigger an evaluation to determine if action is needed. Details on the establishment and monitoring of quality tolerance limits will be provided in a Quality Tolerance Limit Management Plan.

2.3.5. Site Inspections

Site visits will be conducted by the Sponsor or an authorized representative for inspection of study data, participants' medical records, and eCRFs. The Investigator will permit national and local Health Authorities, Sponsor monitors, representatives, and collaborators, and the IRBs/ECs to inspect facilities and records relevant to this study.

3. ADMINISTRATIVE STRUCTURE

For information of the Joint Monitoring Committee, see Section 4.1.3 of the protocol.

4. STUDY AND SITE CLOSURE

The Sponsor (or designee) has the right to close the study site or terminate this study at any time. Reasons for terminating the study may include, but are not limited to, the following:

- The incidence or severity of adverse events in this or other studies indicates a potential health hazard to participants.
- Participant enrollment is unsatisfactory.

The Sponsor will notify the Investigator and Health Authorities if the study is placed on hold, or if the Sponsor decides to discontinue the study or development program.

Study sites will be closed upon study completion. A study site is considered closed when all required documents and study supplies have been collected and a study-site closure visit has been performed.

The Investigator may initiate study-site closure at any time, provided there is reasonable cause and sufficient notice is given in advance of the intended termination.

Reasons for the early closure of a study site by the Sponsor or Investigator may include but are not limited to:

- Failure of the Investigator to comply with the protocol, the requirements of the IRB/IEC or local Health Authorities, the Sponsor's procedures, or GCP guidelines.
- Inadequate recruitment of participants by the Investigator.
- Discontinuation of further study treatment development.

Appendix 2

Adverse Events: Definitions and Procedures for Evaluating, Follow-up and Reporting

1. DEFINITION OF ADVERSE EVENTS

According to the E2A ICH guideline for Good Clinical Practice, an **adverse event** is any untoward medical occurrence in a participant or clinical investigation participant administered a pharmaceutical product and which does not necessarily have to have a causal relationship with this treatment.

An adverse event can therefore be:

- Any unfavorable and unintended sign (including an abnormal laboratory finding), symptom, or disease temporally associated with the use of a medicinal product, whether or not considered related to the medicinal product.

Events Meeting the AE Definition:

- Deterioration in a laboratory value (hematology, clinical chemistry, or urinalysis) or other clinical test (e.g., ECG, X-ray) that is associated with symptoms or leads to a change in study treatment or concomitant treatment or discontinuation from study treatment (see [Appendix 3](#), Section 4).
- Exacerbation of a chronic or intermittent pre-existing condition, including either an increase in frequency and/or intensity of the condition.
- New conditions detected or diagnosed after study treatment administration even though it may have been present before the start of the study.
- Adverse events that are related to a protocol-mandated intervention, including those that occur prior to assignment of study treatment (e.g., screening invasive procedures such as biopsies).
- "Lack of efficacy" or "failure of expected pharmacological action" per se will not be reported as an AE or SAE unless the progression is unexpectedly accelerated and not in line with the natural history of the disease. If the "Lack of efficacy" would not require safety reporting such instances will be captured in the efficacy assessments. However, the signs, symptoms, and/or clinical sequelae resulting from lack of efficacy will be reported as AE or SAE if they fulfill the definition of an AE or SAE.

Events NOT Meeting the AE Definition:

- Any clinically significant abnormal laboratory findings or other abnormal safety assessments which are associated with the underlying disease, unless judged by the Investigator to be more severe than expected for the participant's condition.
- The disease/disorder being studied or expected progression, signs, or symptoms of the disease/disorder being studied, unless more severe than expected for the participant's condition.

- Medical or surgical procedure (e.g., endoscopy, appendectomy): the condition that leads to the procedure is an AE.
- Situations where an untoward medical occurrence did not occur (social and/or convenience admission to a hospital).
- Anticipated day-to-day fluctuations of pre-existing disease(s) or condition(s) present or detected at the start of the study that do not worsen.

2. DEFINITION OF SERIOUS ADVERSE EVENTS

If an event is not an AE per definition above, then it cannot be a serious adverse event (SAE) even if serious conditions are met (e.g., hospitalization for signs/symptoms of the disease under study, death due to progression of disease).

A serious adverse event is defined as any untoward medical occurrence that at any dose:

- **Results in death.**
- **Is life-threatening.**

The term "life-threatening" in the definition of "serious" refers to an event in which the participant was at risk of death at the time of the event; it does not refer to an event which hypothetically might have caused death if it was more severe.

- **Requires inpatient hospitalization or prolongation of existing hospitalization** (see [Appendix 3](#)).

In general, hospitalization signifies that the participant has been admitted to the hospital or emergency ward for observation and/or treatment that would not have been appropriate in the physician's office or outpatient setting. Complications that occur during hospitalization are AEs. If a complication prolongs hospitalization or fulfills any other serious criteria, the event is serious. When in doubt as to whether "hospitalization" occurred or was necessary, the AE should be considered serious.

Hospitalization for elective treatment of a pre-existing condition that did not worsen from baseline is not considered an AE.

- **Results in persistent or significant disability/incapacity**

Disability means substantial disruption of the participant's ability to conduct normal life functions.

This definition is not intended to include experiences of relatively minor medical significance such as uncomplicated headache, nausea, vomiting, diarrhea, influenza, and accidental trauma (e.g., sprained ankle) which may interfere with or prevent everyday life functions but do not constitute a substantial disruption.

- **Is a congenital anomaly/birth defect.**
- **Other significant events:**

Medical or scientific judgment should be exercised in deciding whether SAE reporting is appropriate in other situations such as important medical events that may not be immediately life-threatening or result in death or hospitalization but may jeopardize the participant or may require medical or surgical intervention to prevent one of the other outcomes listed in the above definition. These events should usually be considered serious.

Examples of such events include invasive or malignant cancers, intensive treatment in an emergency room or at home for allergic bronchospasm, blood dyscrasias or convulsions that do not result in hospitalization, or development of drug dependency or drug abuse.

3. RECORDING OF ADVERSE EVENT AND/OR SERIOUS ADVERSE EVENT

When an AE/SAE occurs, it is the responsibility of the Investigator to review all documentation (e.g., hospital progress notes, laboratory reports, and diagnostics reports) related to the event.

The Investigator will then record all relevant AE/SAE information in the CRF.

It is **not** acceptable for the Investigator to send photocopies of the participant's medical records to Medical Monitor in lieu of completion of the eCRF.

There may be instances when copies of medical records for certain cases are requested by the Sponsor. In this case, all participant identifiers, with the exception of the participant number, will be redacted on the copies of the medical records before submission to the Sponsor.

The Investigator will attempt to establish a diagnosis of the event based on signs, symptoms, and/or other clinical information. Whenever possible, the diagnosis (not the individual signs/symptoms) will be documented as the AE/SAE.

3.1. ASSESSMENT OF SEVERITY

The terms "severe" and "serious" are not synonymous. Severity refers to the intensity of an adverse event (rated as mild, moderate, or severe, or according to a pre-defined grading criteria [e.g., National Cancer Institute Common Terminology Criteria for Adverse Events [NCI CTCAE] criteria); the event itself may be of relatively minor medical significance (such as severe headache without any further findings).

Severity and seriousness need to be independently assessed for each adverse event recorded on the eCRF.

Serious adverse events are required to be reported by the Investigator to the Sponsor immediately (i.e., no more than 24 hours after learning of the event).

The adverse event severity grading scale for the NCI CTCAE (v5.0) will be used for assessing adverse event severity. [Table 1](#) will be used for assessing severity for adverse events that are not specifically listed in the NCI CTCAE.

Table 1 Adverse Event Severity Grading Scale

Grade	Severity
1	Mild; asymptomatic or mild symptoms; clinical or diagnostic observations only; or intervention not indicated
2	Moderate; minimal, local, or non-invasive intervention indicated; or limiting age-appropriate instrumental activities of daily living ^a
3	Severe or medically significant, but not immediately life-threatening; hospitalization or prolongation of hospitalization indicated; disabling; or limiting self-care activities of daily living ^{b,c}
4	Life-threatening consequences or urgent intervention indicated ^d
5	Death related to adverse event ^d

NCI CTCAE = National Cancer Institute Common Terminology Criteria for Adverse Events.

Note: Based on the NCI CTCAE (v5.0), which can be found at:

https://ctep.cancer.gov/protocolDevelopment/electronic_applications/docs/CTCAE_v5_Quick_Reference_8.5x11.pdf

- ^a Instrumental activities of daily living refer to preparing meals, shopping for groceries or clothes, using the telephone, managing money, etc.
- ^b Examples of self-care activities of daily living include bathing, dressing and undressing, feeding one's self, using the toilet, and taking medications, as performed by patients who are not bedridden.
- ^c If an event is assessed as a "significant medical event," it must be reported as a serious adverse event (see [Section 6](#) of this appendix for reporting instructions), per the definition of serious adverse event in [Section 2](#).
- ^d Grade 4 and 5 events must be reported as serious adverse events (see [Section 6](#) for reporting instructions), per the definition of serious adverse event in [Section 2](#). Grade 4 laboratory abnormalities would only be reported as SAEs if these meets one or more of the conditions outlined in [Section 2](#) (Definition of Serious Adverse Events) of this appendix.

3.2. ASSESSMENT OF CAUSALITY

Investigators should use their knowledge of the participant, the circumstances surrounding the event, and an evaluation of any potential alternative causes to determine whether an adverse event is considered to be related to the study treatment, indicating "yes" or "no" accordingly. The following guidance should be taken into consideration:

- Temporal relationship of event onset to the initiation of study treatment.
- Course of the event, considering especially the effects of discontinuation of study treatment, or reintroduction of study treatment.
- Known association of the event with the study treatment or with similar treatments.
- Known association of the event with the disease under study.

- Presence of risk factors in the participant or use of concomitant medications known to increase the occurrence of the event.
- Presence of non-treatment-related factors that are known to be associated with the occurrence of the event.

For participant receiving combination therapy, causality will be assessed individually for each protocol-mandated therapy.

4. FOLLOW-UP OF AES AND SAES

The Investigator is obligated to perform or arrange for the conduct of supplemental measurements and/or evaluations as medically indicated or as requested by the Medical Monitor to elucidate the nature and/or causality of the AE or SAE as fully as possible. This may include additional laboratory tests or investigations, histopathological examinations, or consultation with other health care professionals.

If a participant dies during participation in the study or during a recognized follow-up period, the Investigator will provide the Sponsor with a copy of any post-mortem findings including histopathology.

New or updated information will be recorded in the originally completed eCRF.

The Investigator will submit any updated SAE data to the Sponsor within 24 hours of receipt of the information.

5. IMMEDIATE REPORTING REQUIREMENTS FROM INVESTIGATOR TO SPONSOR

Certain events require immediate reporting to allow the Sponsor to take appropriate measures to address potential new risks in a clinical trial. The Investigator must report such events to the Sponsor immediately; under no circumstances should reporting take place more than 24 hours after the Investigator learns of the event. The following is a list of events that the Investigator must report to the Sponsor within 24 hours after learning of the event, regardless of relationship to study treatment:

- Serious adverse events
- Non-serious adverse events of special interest (NSAESI)
- Pregnancies (see Section [8.3.5](#)).

The Investigator must report new significant follow-up information for these events to the Sponsor immediately (i.e., no more than 24 hours after becoming aware of the information). New significant information includes the following:

- New signs or symptoms or a change in the diagnosis.
- Significant new diagnostic test results.

- Change in causality based on new information.
- Change in the event's outcome, including recovery.
- Additional narrative information on the clinical course of the event.

Investigators must also comply with local requirements for reporting serious adverse events to the local Health Authority and IRB/EC.

5.1 REPORTING REQUIREMENTS OF SERIOUS ADVERSE EVENTS, AND NON-SERIOUS ADVERSE EVENTS OF SPECIAL INTEREST

Events that Occur prior to Study Treatment Initiation

After informed consent has been obtained but prior to initiation of study treatment, only serious adverse events caused by a protocol-mandated intervention should be reported. The Serious Adverse Event/Adverse Event of Special Interest Reporting Form provided to Investigators should be completed and submitted to the Serious Adverse Event Responsible immediately (i.e., no more than 24 hours after learning of the event).

Events that Occur after Study Treatment Initiation

For reports of serious adverse events and non-serious adverse events of special interest (Section 8.3.6) that occur after initiation of study treatment (Section 8.3.1), Investigators should record all case details that can be gathered immediately (i.e., within 24 hours after learning of the event) on the appropriate Adverse Event of Special Interest/Serious Adverse Event eCRF form and submit the report via the electronic data capture (EDC) system. A report will be generated and sent to the Sponsor's Safety Risk Management department.

In the event that the EDC system is unavailable, the Serious Adverse Event/Adverse Event of Special Interest Reporting Form provided to Investigators should be completed and submitted to the Serious Adverse Event Responsible immediately (i.e., no more than 24 hours after learning of the event).

Once the EDC system is available, all information will need to be entered and submitted via the EDC system.

Reporting of Post-Study Adverse Events and Serious Adverse Events

After the end of the adverse event reporting period (see Section 8.3.1), all deaths, regardless of cause, should be reported through use of the Long-Term Survival Follow-Up eCRF.

In addition, if the Investigator becomes aware of a SAE that is believed to be related to prior study treatment, the event should be reported directly to the Sponsor or its designee, either by faxing or by scanning and emailing the SAE Reporting Form using the fax number or email address provided to Investigators.

5.2 REPORTING REQUIREMENTS FOR CASES OF ACCIDENTAL OVERDOSE

Accidental overdose and medication error (hereafter collectively referred to as "special situations"), are defined as follows:

- Accidental overdose: accidental administration of a drug in a quantity that is higher than the assigned dose.
- Medication error: accidental deviation in the administration of a drug.
 - In some cases, a medication error may be intercepted prior to administration of the drug.

Special situations are not in themselves adverse events, but may result in adverse events. Each adverse event associated with a special situation should be recorded separately on the Adverse Event eCRF. If the associated adverse event fulfills seriousness criteria, the event should be reported to the Sponsor immediately (i.e., no more than 24 hours after learning of the event). For this study, adverse events associated with special situations should be recorded as described below for each situation:

- Accidental overdose: Enter the adverse event term. Check the "Accidental overdose" and "Medication error" boxes.
- Medication error that does not qualify as an overdose: Enter the adverse event term. Check the "Medication error" box.
- Medication error that qualifies as an overdose: Enter the adverse event term. Check the "Accidental overdose" and "Medication error" boxes.

In addition, all special situations associated with the study drugs, regardless of whether they result in an adverse event, should be recorded on the Adverse Event eCRF and should be recorded as described below:

- Accidental overdose: Enter the "Blinded Drug" and "accidental overdose" as the event term. Check the "Accidental overdose" and "Medication error" boxes.
- Medication error that does not qualify as an overdose: Enter the name of the drug administered and a description of the error (e.g., wrong dose administered, wrong dosing schedule, incorrect route of administration, wrong drug, expired drug administered) as the event term. Check the "Medication error" box.
- Medication error that qualifies as an overdose: Enter the drug name and "accidental overdose" as the event term. Check the "Accidental overdose" and

"Medication error" boxes. Enter a description of the error in the additional case details.

- Intercepted medication error: Enter the drug name and "intercepted medication error" as the event term. Check the "Medication error" box. Enter a description of the error in the additional case details.

As an example, an accidental overdose that resulted in a headache would require the completion of two Adverse Event eCRF pages, one to report the accidental overdose and one to report the headache. The "Accidental overdose" and "Medication error" boxes would need to be checked on both eCRF pages.

6. EXPEDITED REPORTING TO HEALTH AUTHORITIES, INVESTIGATORS, INSTITUTIONAL REVIEW BOARDS, AND ETHICS COMMITTEES

The Sponsor will promptly evaluate all serious adverse events and NSAESI against cumulative product experience to identify and expeditiously communicate possible new safety findings to Investigators, IRBs, ECs, and applicable Health Authorities based on applicable legislation.

To determine reporting requirements for single adverse event cases, the Sponsor will assess the expectedness of these events through use of the reference safety information in the documents listed below:

Drug	Document
RO7121661	RO7121661 Investigator's Brochure
RO7247669	RO7247669 Investigator's Brochure
Nivolumab	EU SmPC

The Sponsor will compare the severity of each event and the cumulative event frequency reported for the study with the severity and frequency reported in the applicable reference document.

Reporting requirements will also be based on the Investigator's assessment of causality and seriousness, with allowance for upgrading by the Sponsor as needed.

Appendix 3

Procedures for Recording Adverse Events

Investigators should use correct medical terminology/concepts when recording AEs on the Adverse Event eCRF. Avoid colloquialisms and abbreviations.

Only one AE term should be recorded in the event field on the Adverse Event eCRF.

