4.1.4 Scientific Rationale for Study Design

The study rationale is provided in Section 2.1.

In this study, the primary efficacy endpoints will be OS. This study will test the hypothesis that treatment with RO7247669 will prolong OS compared to treatment with nivolumab. Improvement in OS is generally accepted as the best measure of clinical benefit for patients with solid tumors. Prior studies with anti-PD1 treatments in 2L CPI-naïve ESCC showed inconsistent results for other commonly used endpoints such as ORR and PFS, which do not necessarily correlate with the observed OS benefits.

This study is blinded. Investigators, site staff, and participants will be unaware of the treatment allocation. Rationale for the blinded design is reducing potential bias in the assessment of disease recurrence/progression, PROs, and safety.

Nivolumab was chosen as active comparator for this study (Section 2.2.5). Given the positive data and approval of nivolumab for patients with ESCC after prior fluoropyrimidine- and platinum-based chemotherapy, independent of PDL1 expression, nivolumab was considered the best comparator for the anticipated patient population in this study.

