6.3.2 Blinding

Investigators and participants will remain blinded to each participant's assigned study treatment throughout the course of the study. In order to maintain this blind, an otherwise uninvolved, unblinded pharmacist will be responsible for the reconstitution and dispensation of all study treatment and will endeavor to ensure that there are no differences in time taken to dispense following randomization. Because of the size of the study, use of IxRS, randomization, blinding, and expected lack of substantial emergency unblinding, collected data will be protected from any biases that would arise from subjectivity in the reporting of the outcome measures. To further protect the integrity of the study, the results of interim safety and efficacy analyses will not be made known to the Investigators.

Treatment codes should not be broken except in emergency situations. *This includes the decision to stop recruitment into the RO7121661 arm of the study. The study will not be unblinded and patients already randomized to the RO7121661 arm prior to this decision will continue to receive treatment with RO7121661.* If the Investigator wishes to know the identity of the study drug for any other reason, the Investigator should contact the Medical Monitor directly.

If emergency unblinding is necessary for participant management (e.g., in the case of a serious AE (SAE) for which participant management might be affected by knowledge of treatment assignment), the Investigator will be able to break the treatment code by contacting the IxRS. This emergency unblinding may occur without prior authorization from the Sponsor. However, the Investigator should document and provide an explanation to the Sponsor for any premature unblinding (e.g., unblinding due to an SAE or accidental unblinding).

As per Health Authority reporting requirements, the Sponsor's drug safety representative will break the treatment code for all serious, unexpected suspected adverse reactions that are considered by the Investigator or Sponsor to be related to study drug. The participant may continue to receive treatment, and the Investigator and participant will remain blinded to treatment assignment.

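### Appendix 2, Section 5.2 masks the drug in one of its four special-situation entries and asks for its name in the other three, in conflict with the blinding rules

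*Combined protocol and SAP*

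**What the plan says.** Appendix 2, Section 5.2 groups accidental overdose and medication error as special situations. It asks that "all special situations associated with the study drugs, regardless of whether they result in an adverse event, should be recorded on the Adverse Event eCRF". Four entries then set the event term:

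- Accidental overdose: "Enter the 'Blinded Drug' and 'accidental overdose' as the event term".
- Medication error that is not an overdose: "Enter the name of the drug administered and a description of the error".
- Medication error that is an overdose: "Enter the drug name and 'accidental overdose' as the event term".
- Intercepted medication error: "Enter the drug name and 'intercepted medication error' as the event term".

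On who fills in the form, Appendix 2, Section 3 says: "The Investigator will then record all relevant AE/SAE information in the CRF". Section 8.3 extends the duty to qualified designees of the Investigator.

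On the blind, Section 4.1.4 states that "Investigators, site staff, and participants will be unaware of the treatment allocation", and gives as the reason the risk of bias in judging progression, in patient-reported outcomes and in safety. Section 6.3.2 adds that "Investigators and participants will remain blinded" for the whole study. It limits breaking the code to emergencies, and sends an Investigator who wants the identity for another reason to the Medical Monitor. Section 6.4 keeps the Drug Accountability Record out of reach of blinded site personnel and the blinded monitor. Section 8.5 withholds from sites any drug concentrations that would unblind.

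**The concern.** Three of the four entries ask for the item of information that the rest of the protocol takes care to keep from the site. The masked term in the first entry shows that the need was recognised in this very list, but the other three were not brought into line with it. Someone who follows them literally has to find out which drug the participant was given, and then types it on an adverse event page.

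What is at stake is the blind for the participant concerned. Progression and response are assessed by the Investigator, and central blinded review is only optional (Section 8.1.1). The Investigator also judges whether an adverse event is related to treatment (Appendix 2, Section 3.2), and participants complete the quality-of-life and symptom questionnaires themselves. All of these can shift once the arm is known.

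**Working it through.** No calculation applies: the plan gives no figure on this point. The check is to set the four entries beside the rules they must fit.

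| Entry in Appendix 2, Section 5.2 | Boxes ticked | Drug identity asked for |
|---|---|---|
| Accidental overdose | Overdose and medication error | Masked |
| Medication error, not an overdose | Medication error | Named |
| Medication error that is an overdose | Overdose and medication error | Named |
| Intercepted medication error | Medication error | Named |

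Count: 1 of 4 entries is masked, 3 of 4 name the drug.

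**Consistency within the list.** Section 5.2 defines accidental overdose as the accidental giving of more than the assigned quantity, and medication error as an accidental deviation in giving a drug. An accidental overdose therefore also meets the definition of a medication error that is an overdose. The first and third entries tick the same two boxes and use the same overdose term, yet one masks the drug and the other names it. A site faced with one such event has two opposite instructions.

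**Consistency with the blind.** The person responsible for the entry is the Investigator or a designee. The Investigator is to stay unaware of allocation. The name is held by the unblinded pharmacist and on the restricted record in Section 6.4. So a blinded Investigator has three courses: leave the term incomplete, borrow the masked term from the first entry although the text does not say so, or obtain the name. Section 5.2 does not choose between them. It names no restricted eCRF page, no unblinded form and no unblinded person, and nothing elsewhere in the documents supplies one.

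**What a name would reveal.** For a wrong dose, schedule or route, or an expired vial, the drug named would normally be the assigned one. For a wrong drug, the name is that of the drug given, which need not be the assigned arm. For an intercepted error the participant received nothing in error, so the disclosure has no evident use in managing the participant.

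**Free text.** The error description can disclose the arm even when the drug is masked. Table 6 gives 2100 mg for both bispecific antibodies, supplied as 300 mg vials, and 240 mg for nivolumab, supplied as one 240 mg vial. That is 2100 / 300 = 7 vials against 240 / 240 = 1. A dose of 240 mg points to nivolumab. A dose of 2100 mg points to RO7247669 for anyone randomised after the RO7121661 arm closed, and to one of two arms for those randomised before.

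**How many participants.** The documents give no medication-error rate. The planned enrolment of 255 in Section 9.1 has been re-estimated and the new figure is redacted. No count can be derived.

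**The case against.** The strongest reply is that the text cannot be carried out as a code break and so would not work as one. A blinded Investigator does not know the name, Section 5.2 does not authorise anyone to break the code, and Section 6.3.2 forbids it outside emergencies. Read together, a sensible site would write 'Blinded Drug' throughout. Section 6.3.2 also offers a controlled route through the Medical Monitor and requires any premature unblinding to be documented and explained. An unblinded pharmacist is on site, is well placed to notice wrong, expired or intercepted drug, and might be the one to complete the entry.

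Much of this stands as a limit on the consequence. It does not remove the defect. The contrast between the first entry and the other three invites the opposite of the sensible reading. The Medical Monitor route serves an Investigator who wishes to know the drug; it is not described as a routine step in form completion, and Section 5.2 does not point to it. Section 6.3.2 describes the pharmacist as otherwise uninvolved, and no section gives that person this task.

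A reader might infer that following the instruction unblinds the site, or breaks the blind for every participant with a medication error. The documents do not support that. Disclosure would concern one participant per recorded error, would occur only if the wording is followed literally, and in a wrong-drug error need not reveal the assigned arm. Nor do the documents describe who can read which eCRF page, so how far an entered name would travel is unknown. The Pharmacy Manual, to which Section 6.4 refers for details, was not available and may settle some of this.

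**Conclusion.** The point holds as a minor but real fault. Three of the four entries in Appendix 2, Section 5.2 are wrong as written for a blinded trial: they contradict the first entry and do not fit Sections 4.1.4, 6.3.2 and 6.4. The certain consequence is an entry that blinded staff cannot complete as instructed. Unblinding of the individual participant is a possible consequence, not a certain one.

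The number affected is likely to be small and cannot be put into figures. The effect on the primary endpoint, death from any cause, is negligible. Investigator-assessed PFS and response, patient-reported outcomes and causality judgements are more exposed, but only for the participants concerned. The conclusion assumes that the Investigator or a blinded designee completes the entry and that no document outside the protocol already supplies a masked term.

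**What to change.** In Appendix 2, Section 5.2, use 'Blinded Drug' in the three entries that now ask for the drug name, to match the accidental-overdose entry. Keep the identity of the drug on the restricted Drug Accountability Record of Section 6.4, or on an unblinded form completed by the unblinded pharmacist. For a wrong-drug error, that record should show both the drug assigned and the drug given. Add a note to the eCRF completion guidelines telling sites to leave arm-revealing details, such as a dose in mg or a vial count, out of the free-text description and to pass them by the unblinded route. Check the Pharmacy Manual for consistency at the same time.

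The cost is three wording changes and one guideline note. No dose, schedule or clinical rule changes, and no analysis is affected.
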